## 6.2 Disallowed Medications and Supplements

The following medications will not be allowed during the study:

- Selective and non-selective MAO inhibitors including those whose primary mechanism of action is not monoamine oxidase inhibition: phenelzine, rasagiline, selegiline, procarbazine, isocarboxazid, tedizolid, tranylcypromine, syrian rue, linezolid, methylene blue, moclobemide
- Initiation of any antidepressants, antipsychotics, or anxiolytics.
- Azelastine
- Conivaptan
- Dapoxetine
- Fusidic Acid
- Idelasib
- Orphenadrine
- Paraldehyde
- Thalidomide
- Grapefruit juice, ginkgo biloba, St. John's wort, and ginseng (which interfere with study drug metabolism).
- Initiation of any new PD medications and increases in the dosage of existing PD medications will be prohibited.
- Participants will also be prohibited from beginning any form of psychotherapy following study entry.

If treatment with a disallowed medication is required, the study drug should be discontinued and the participant should continue in the study off of the study drug. The study drug may be restarted after the disallowed medication is stopped.

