We recognize the potential for anxiety to not improve or worsen, particularly among those participants in the placebo arm, and that this may have a negative effect on their quality of life. However, we believe that the benefits of including a placebo arm for blinding and to allow for calibration of baseline assumptions regarding intolerability outweigh the potential risks. We will institute measures to ensure the safety of all participants. Of note, participants will not be asked to discontinue any pre-existing anxiolytics or antidepressants (with the exception of MAO inhibitors which pose a potential safety concern) or discontinue psychotherapy to participate in the study. Participants will only be asked not to increase the dosage of pre-existing anxiolytics or antidepressants, start new anxiolytics or antidepressants, or initiate psychotherapy for the duration of the study. Investigators will exclude from participation any patients where there is a concern for patient safety. If a participant's anxiety symptoms worsen significantly during the course of the study or if he/she develops suicidal ideation, which is deemed severe enough to reflect a significant suicidal risk, we will terminate the participant from the study and we will immediately refer the patient to a mental health provider for treatment. The investigator will determine the most appropriate referral, which may be referral to an outpatient mental health provider or referral to the Comprehensive Psychiatric Emergency Program. Participants and their caregivers will be encouraged to contact the investigators at any time if there is concern about worsening anxiety or adverse experiences.

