#### **During the Study:**

- The addition of new anti-parkinsonian medications or increase in dosage of existing anti-parkinsonian medications will be prohibited for the duration of the trial.
- The addition of a new anxiolytic or antidepressant or increase in dosage of an existing anxiolytic or antidepressant will be prohibited for the duration of the trial.
- Participants will not be allowed to initiate or discontinue psychotherapy following enrollment. If they are participating in it at the time of enrollment, it should be continued for the duration of the study.

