## **6.0 CONCOMITANT AND DISALLOWED MEDICATIONS**

### **6.1 Allowed Concomitant Medications**

Enrolling participants may be on PD medications, with the exception of monoamine oxidase inhibitors. The dosage must be stable for 30 days prior to the baseline visit.

No new PD medications may be initiated for the duration of the study and no increases in the dosages of current PD medications will be allowed.

Enrolling participants may be on antidepressants (with the exception of monoamine oxidase inhibitors), antipsychotics, and/or anxiolytics. The dosage must be stable for 30 days prior to the baseline visit and for the duration of the study. The initiation of one of these medications will be prohibited for the duration of the study.

Strong CYP3A4 inhibitors (atazanavir, boceprevir, ceritinib, clarithromycin, cobicistat and cobicistat containing formulations, darunavir, idelalisib, indinavir, itraconazole, ketoconazole, lopinavir, nefazodone, nelfinavir, ombitasvir-paritaprevir-ritonavir, ombitasvir-paritaprevir-ritonavir plus dasabuvir, posaconazole, ritonavir and ritonavir containing formulations, saquinavir, telaprevir, telithromycin, and voriconazole) will be allowed. Participants will be monitored for potential adverse events related to an increase in the serum study drug concentration.

Strong CYP3A4 Inducers (carbamazepine, enzalutamide, fosphenytoin, lumacaftor, mitotaine, phenobarbital, phenytoin, primidone, rifabutin, rifampin, and rifapentine) will be allowed.

Non-dihydropyridine calcium channel blockers (diltiazem, verapamil) and interacting macrolide antibiotics (erythromycin, clarithromycin, and telithromycin) will be allowed. Participants will be monitored for potential adverse events related to an increase in the serum study drug concentration.

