## **7.0 PARTICIPANT WITHDRAWALS**

Participants will be advised in the written informed consent forms that they have the right to withdraw from the study at any time without prejudice. Participants may be withdrawn by the investigator/sponsor for:

- (1) Non-compliance with study drug or procedures
- (2) Receipt of disallowed medications that cannot be discontinued
- (3) An adverse event which in the investigator's judgment puts the participant at risk
- (4) Illness that prevents continued trial participation
- (5) Termination of study funding
- (6) Worsening of anxiety that in the investigator's judgment requires prompt treatment with an alternative therapy

In the event of a premature study withdrawal, a premature termination visit should occur. Evaluations are detailed in section 5.2.6. Participants withdrawn from the study will not be replaced.

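### Section 6.2 ties stopping study drug to starting an anxiolytic or antidepressant but not to increasing one, and section 13.2 has no rescue rule, so the two rescue routes can be scored differently and rescued participants can count as responders

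*Combined protocol and SAP*

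**What the plan says.** **Prohibitions.** Section 2.4: "Participants will only be asked not to increase the dosage of pre-existing anxiolytics or antidepressants, start new anxiolytics or antidepressants, or initiate psychotherapy". Section 3.2, in its list for conduct during the study, states that an "increase in dosage of an existing anxiolytic or antidepressant will be prohibited for the duration of the trial". Section 6.1, on antidepressants, antipsychotics and anxiolytics: "The dosage must be stable for 30 days prior to the baseline visit and for the duration of the study". None of the three says what happens to study drug if the rule is broken.

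**Consequence.** Section 6.2 lists the disallowed treatments. For psychotropic drugs the entry is "Initiation of any antidepressants, antipsychotics, or anxiolytics". For Parkinson's drugs the same list is wider: "Initiation of any new PD medications and increases in the dosage of existing PD medications will be prohibited". If a disallowed medication is needed, "the study drug should be discontinued and the participant should continue in the study off of the study drug". Restart is possible: "The study drug may be restarted after the disallowed medication is stopped". Section 8.2 repeats this and requires the titration schedule to be followed again.

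**Termination and withdrawal.** Section 2.4 ends participation if anxiety worsens significantly. Section 10.2 does so if the participant or the investigator finds the level of anxiety unacceptable. Section 7.0 permits withdrawal for non-compliance, or for worsening anxiety that in the investigator's judgment "requires prompt treatment with an alternative therapy".

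**Analysis.** Section 13.2 counts non-completion on study drug for any reason as intolerability and rejects tolerability at 7 or more failures. It takes HAM-A, HADS, CGI-I and PGI-I at week 12 without mentioning rescue. Last observation carried forward is reserved for loss to follow-up. Section 8.5 keeps participants in follow-up after study drug stops.

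**The concern.** Entry on a stable anxiolytic or antidepressant is allowed, so rescue has two routes: starting a new drug, or raising the dose of one already taken. Read literally, section 6.2 takes the first participant off study drug and says nothing about the second. The first may then be a primary failure and the second a completer, although the clinical event is similar and the difference may come only from what each was taking at entry. In a trial decided by a small count, this should be settled before unblinding and not case by case.

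The second problem does not depend on the first. Participants stay in follow-up after rescue, whether on or off study drug, and their week-12 scores enter the analysis as they stand. A fall in HAM-A produced by another anxiolytic can therefore meet the responder definition and be credited to buspirone or placebo. The stated purpose of these outcomes is to look for a signal that buspirone works.

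**Working it through.** **1. The plan's own figures.** Inputs from sections 13.1 and 13.2: n = 21 on buspirone, rates 20% and 40%, rejection at 7 or more failures. With X binomial(21, p), P(X ≥ 7) = Σ over k = 7 to 21 of C(21,k) p^k (1−p)^(21−k).
- p = 0.40: 0.7998, which is the stated 80% power.
- p = 0.20: 0.1085, slightly above the stated 10%. That is a separate matter.
- Total at 4:1: 21/0.8 = 26.25, rounded up to 27, leaving 27 − 21 = 6 on placebo.

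**2. The two rescue routes side by side.**

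| | Starts an anxiolytic or antidepressant | Increases an existing one |
|---|---|---|
| Prohibited? | Yes (2.4, 3.2, 6.1, 6.2) | Yes (2.4, 3.2, 6.1) |
| On the 6.2 list? | Yes | No |
| Stated consequence for study drug | Stop; restart possible (6.2, 8.2) | None |
| Termination or withdrawal under 2.4, 7.0, 10.2 | Can apply | Can apply |
| Primary result without termination or withdrawal | Failure if not restarted; scoring after restart unstated | Can be a completer |
| Week-12 anxiety outcomes | Used as observed | Used as observed |

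The Parkinson's entry in the same list names both initiation and increases, so the narrower psychotropic entry cannot be read as shorthand for both. Decreases are also unsettled: 2.4 and 3.2 restrict increases only, while 6.1 requires a stable dosage throughout.

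**3. Weight of one participant in the primary count.** 1/21 = 4.8 percentage points. Six failures (6/21 = 28.6%) do not reject tolerability; seven (7/21 = 33.3%) do. One differently classified participant at that boundary reverses the conclusion.

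**4. Illustration for a larger share.** The documents give no rate of rescue by dose increase, so the share q of buspirone participants affected is my assumption.
- Failure rate 40% with the affected participants counted as failures, but they are scored as completers. Power = P(X ≥ 7) at p = 0.40 − q.
- Failure rate 20% without them, but they are scored as failures. Chance of rejection = P(X ≥ 7) at p = 0.20 + q.

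| q (assumed) | Power at 0.40 − q | Rejection at 0.20 + q |
|---|---|---|
| 0 | 0.80 | 0.11 |
| 2% | 0.74 | 0.16 |
| 5% | 0.64 | 0.26 |
| 10% | 0.45 | 0.45 |

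**5. Weight of one rescued responder.** Buspirone: 1/21 = 4.8 points. Placebo: 1/6 = 16.7 points, or 1/5 = 20 points if only 5 are randomised. Section 4.1 speaks of 35 eligible participants, whereas 3.1 includes screen failures in the 35. If 35 were randomised at 4:1 (28 and 7), the figures would be 1/28 = 3.6 and 1/7 = 14.3 points.

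**The case against.** **Worsening anxiety is already handled.** Sections 2.4 and 10.2 end participation for significant or unacceptable worsening, and 7.0 permits withdrawal, whichever rescue is used. Any of these makes a primary failure. A reader might infer from 6.2 that equivalent rescue always gives opposite primary results; these provisions show that it does not. What remains is rescue that does not lead to termination or withdrawal. All three provisions rest on judgment and 7.0 is permissive, so they do not guarantee equal scoring.

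**A starter is not necessarily a failure.** Sections 6.2 and 8.2 allow restart, so a participant who starts a disallowed drug can still finish on study drug. This stands. It also exposes a further gap, because the plan does not say how such an interruption is scored.

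**The primary outcome is completion on study drug, not freedom from rescue.** Someone who finishes on buspirone after raising a benzodiazepine has met the definition as written. This stands too. Forcing identical results would need a common stopping rule, which is a clinical decision, or a different endpoint. The point therefore asks only for a stated scoring rule.

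**Using scores regardless of rescue is a recognised treatment-policy approach.** The outcomes are exploratory, the study is not powered for comparisons between arms, and section 8.6 invokes intention to treat for unblinded participants. However, 13.2 does not say that it adopts this approach for rescue. Reporting both analyses meets the objection. It is also fair that a participant terminated under 2.4 or 10.2 is assessed at the premature termination visit, so that route need not credit later treatment to the arm.

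**Placebo rescue.** A reader might infer that placebo participants need rescue more often and that this hides a real difference. The documents give no rescue rate in either arm, and the synopsis says that buspirone's effectiveness for anxiety in this population is unknown. The inference is not supported.

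**Conclusion.** The point holds in a limited form and should be corrected. Section 6.2 omits dose increases of anxiolytics and antidepressants from the list that carries the study-drug consequence, although other sections prohibit them. Where rescue does not end in termination or withdrawal, the two routes can give different primary classifications, and the scoring of interruption with restart is unstated. Separately, nothing in 13.2 prevents a rescued participant from counting as a week-12 responder for the assigned arm; this gap stands whatever is decided about the first.

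The size is known only per participant. It is 4.8 points in the primary count, assuming 21 on buspirone and the boundary of 7, and 4.8 points (buspirone) or 16.7 to 20 points (placebo, 5 or 6 participants) in a responder proportion. These are simply 1/n. The power and rejection figures for 2% to 10% affected are illustrations on an assumed share, not predictions.

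**What to change.** 1. Reconcile sections 2.4, 3.2, 6.1, 6.2, 7.0 and 10.2 so that starts, increases and decreases of anxiolytics and antidepressants each have a stated consequence. The clinical rule is for the sponsor to decide.
2. In 13.2, state how each rescue route, and interruption of study drug followed by restart, is scored in the primary count.
3. In 13.2, count participants who start or increase an anxiolytic or antidepressant, or begin psychotherapy, before week 12 as non-responders on HAM-A, CGI-I and PGI-I. Report the responder proportions also regardless of rescue, and mean HAM-A and HADS changes with and without post-rescue scores. Participants who are off study drug but not rescued should not become non-responders for that reason alone.

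The cost is a protocol clarification, some analysis wording and a few extra table rows. Concomitant medications are already recorded at every scheduled visit, including the telephone visits. The schedule names no separate item for psychotherapy, so the sponsor should confirm that the health update captures it. The downside is that responder proportions may be slightly lower.

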## **7.0 PARTICIPANT WITHDRAWALS**

Participants will be advised in the written informed consent forms that they have the right to withdraw from the study at any time without prejudice. Participants may be withdrawn by the investigator/sponsor for:

- (1) Non-compliance with study drug or procedures
- (2) Receipt of disallowed medications that cannot be discontinued
- (3) An adverse event which in the investigator's judgment puts the participant at risk
- (4) Illness that prevents continued trial participation
- (5) Termination of study funding
- (6) Worsening of anxiety that in the investigator's judgment requires prompt treatment with an alternative therapy

In the event of a premature study withdrawal, a premature termination visit should occur. Evaluations are detailed in section 5.2.6. Participants withdrawn from the study will not be replaced.

## **8.0 STUDY DRUG ADMINISTRATION/ASSIGNMENT**

### **8.1 Study Drug**

It is the investigator's determination that this study drug is IND exempt.

- Buspirone is lawfully marketed in the United States and is FDA-approved for the treatment of generalized anxiety disorder in the general population.
- There is no intention to use the results of the proposed study to support a new indication or change in labeling for buspirone.
- There is no intention to use the results of the proposed study to support a change in advertisement for buspirone.
- The proposed route of administration (oral) and dosage (up to 30 mg twice daily) are consistent with current prescribing guidelines. There have been prior human studies of buspirone in the Parkinson disease population. One very small study indicated that use of buspirone dosages consistent with current prescribing guidelines might be associated with worsening of PD motor function however three studies showed no worsening of PD motor function at the same dosages. The proposed study is designed to determine the tolerability of buspirone in this population. Adverse events will be closely monitored. Buspirone is generally well tolerated and there is no reason to believe that using the medication for the treatment of anxiety in the PD population would significantly increase the risks associated with use of the drug.
- The study will be conducted only after approval by my institutional IRB and participants will be required to provide informed consent.

The buspirone label is included in RSRB application section 50.1 and can be found at [http://www.accessdata.fda.gov/drugsatfda\\_docs/nda/2000/21-190\\_BuSpar\\_Prntlbl.pdf](http://www.accessdata.fda.gov/drugsatfda_docs/nda/2000/21-190_BuSpar_Prntlbl.pdf).

The Investigational Drug Service at the University of Rochester will manage the over-encapsulation, packaging, and distribution of the study drug and placebo in conjunction with an un-blinded study team member. 5 mg tablets of the study drug will be purchased in bulk from Teva Pharmaceutical. The study drug will be over-encapsulated and repackaged into labeled bottles. In order to account for the necessary titration step with dosage increases (as described in section 5.1.2) the Investigational Drug Service will dispense bottles containing 6 capsules (to cover the 3-day titration period) and 34 capsules (to cover the maintenance period). In the event of dosage escalation beyond 7.5 mg study drug/placebo, participants will be provided with two bottles, one to cover the titration period and one to cover the maintenance period, at each dispensation and carefully instructed as to which bottle to begin with. Double panel medication labels will be provided by the Investigational Drug Service and labeling will include the study number, dosage, route of administration, quantity, directions for use, storage conditions, and additional space for information to be completed by a study team member (dispensing date, participant number). The unblinded team member will remove the outer panel, which will specify whether the bottle contains study drug or placebo, to reveal the inner panel which will not include this specification.

The drug will be stored at the site in a locked storage area with controlled temperature (59° - 86° F).

At each in-person visit and following each telephone visit, participants will receive a 20 day supply of study drug, which will ensure that participants have an adequate supply of study drug until their next visit.

## **8.2 Dosage of Study Drug**

The study drug will be administered orally. Participants will initially receive buspirone 7.5 mg or matching placebo twice daily. Investigators will evaluate the participants at two-week intervals and make dosage adjustments as necessary and tolerated up to a maximum of 30 mg twice daily to achieve an optimal dosage that balances efficacy with tolerability. The investigator will be allowed to decrease the dosage or not escalate the dosage if there are adverse events. The titration schedule and parameters for dosage adjustment are detailed in section 5.1.

In the event of study drug discontinuation due to treatment with a disallowed medication, the study drug may be re-started following discontinuation of the disallowed medication and the same titration schedule and parameters for dosage adjustment should be followed (as specified in section 5.1.2).

## **8.3 Participant Enrollment/Randomization**

We will use computer-generated randomization with participants randomized in a 4:1 ratio to study drug or placebo. Randomization will be managed by the statistician.

## **8.4 Accountability of Investigational Supplies**

The Investigational Drug Service and on-site personnel will share responsibility for control of the study drug. The Investigational Drug Service will be responsible for

dispensing labeled supplies of study drug to the study site. The study coordinator will be responsible for acknowledging the receipt of study drug within 48 hours. The study coordinator and Investigational Drug Service will maintain accurate records of all supplies dispensed/received. Prior to dispensation to the participant, an un-blinded study team member will remove the outer panel of the double panel label on the drug bottle(s) and place this on the Drug Dispensing/Return Log. The un-blinded study team member will be a study coordinator who will not have any role in data collection. All study drug supplies issued to, used by, and returned by each participant must be recorded on the Drug Dispensing/Return Log. Participants will return all unused study drug, including empty bottles. After reconciliation, all remaining study supplies may be destroyed as per institutional policy.

The Investigational Drug Service and study coordinators will communicate regularly regarding study drug supply.

### **8.5 Participant Withdrawal of Study Drug**

Participants who discontinue study drug and do not withdraw their consent, will continue to be followed in the study.

### **8.6 Emergency Drug Disclosure**

The study team will be provided with individually sealed envelopes for each participant containing the treatment assignment. All sealed envelopes will be returned to the statistician at the conclusion of the study and will be inspected to ensure that they have not been opened. A participant's envelope should be opened only in the event of a medical emergency. Treatment assignment may be revealed if the investigator feels that study drug discontinuation is insufficient and knowledge about treatment assignment and/or dosage is required to ensure the safety of the participant. If a drug disclosure is made, a record must be made by the investigator detailing the purpose, date, and personnel involved. The participant will be withdrawn from further exposure to study medication. In accordance with the intention-to-treat principle, these participants will be encouraged to remain in the study and every attempt will be made to continue to follow them and obtain data.

